7.2.1.2.4 Relatedness of Study Agent to Adverse Event

The investigator (or an authorized study physician) or sponsor must submit an attribution for the relatedness of the reported AE to the study agent. The attribution should take into account both the temporal association and any known physical, physiological, or toxicological information regarding the study agent that could reasonably infer causality. The three attribution categories are:

- **Definite** - Clearly related to the study agent. An adverse event that follows a temporal sequence from administration of the study agent; follows a known response pattern to study agent; and, when appropriate to the protocol, is confirmed by improvement after stopping the study agent (positive rechallenge; and by reappearance of the reaction after repeat exposure (positive rechallenge)); and cannot be reasonably explained by known characteristics of the subject's clinical state or by other therapies.
- **Possibly** - May be related to the study agent. An adverse event that follows a reasonable temporal sequence from administration of study agent and follows a known response pattern to the study agent, but could have been produced by the subject' clinical state or by other therapies.
- **Unrelated** - Clearly NOT related to the study agent. An adverse event that does not follow a reasonable temporal sequence after administration of the study agent and most likely is explained by the subject's clinical disease state or by other therapies. In addition, a negative rechallenge to the study agent would support an unrelated relationship.

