2.2 RATIONALE

Alkahest study ALK4290-201 will evaluate 400 mg of ALK4290 administered orally twice a day for a total dose of 800 mg. ALK4290 is a highly specific and potent small molecule antagonist of the human C-C chemokine receptor type 3 (CCR3). The CCR3/eotaxin axis is a key chemotactic factor for eosinophils, mast cells, and, in the context of wAMD, endothelial cells. Inhibiting CCR3 interrupts endothelial cell migration, thereby reducing the morphological changes (e.g., central retinal thickness (CRT), edema, and blood leakage) attributed to pathologic CNV ([Nagai 2015](#)). The anticipated clinical results from an orally administered CCR3 antagonist therapy would be to maintain or, potentially, improve visual acuity, enhance quality of life, and reduce the need for IVT injections.

[figure not shown]
Although a significant amount of preclinical data exists for CCR3 blockade in wAMD, there is no published clinical data supporting the therapeutic use of CCR3 in wAMD ([Nagai 2015](#), [Wang 2016](#), [Wang 2011](#)) (for further details and information, see the [REDACTED] for ALK4290). This study is designed to demonstrate a therapeutic effect of ALK4290 on BCVA in wAMD subjects. Without treatment, patients with wAMD lose an average of 10 ETDRS letters within 1 year and eventually most patients become legally blind. The current standard of care for wAMD is IVT anti-VEGF therapy which usually maintains and improves BCVA. Despite anti-VEGF therapy, one sixth of patients progress to blindness. In addition, IVT injections are burdensome and expensive for patients and the healthcare system, and may be associated with serious adverse events (e.g., endophthalmitis, retinal detachment, traumatic cataract, and IOP). High concentrations of anti-VEGF may have deleterious long-term consequences for the integrity of the retina and the RPE.

Hence, an equally effective oral maintenance treatment, or an oral treatment that provides incremental improvement in

BCVA compared to anti-VEGF therapy, would be considered a substantial medical advance. The aim of this 6-week trial is to investigate whether orally administered ALK4290 has the potential to maintain or increase BCVA as measured by ETDRS. If a favorable effect on BCVA is observed, this study would potentially provide the basis for a longer-term evaluation of the effects of ALK4290 to further assess functional and morphological benefits.

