14.2.7.2	Presence of Leakage from Choroidal Neovascularization as Demonstrated by Fluorescein Angiography in the Study Eye at Scheduled Visits	PP Set
14.2.7.3	Summary of Size of Leakage from Choroidal Neovascularization (Number of Disc Areas) and Change from Baseline as Demonstrated by Fluorescein Angiography in the Study Eye at Scheduled Visits	Evaluable Set
14.2.7.4	Summary of Size of Leakage from Choroidal Neovascularization (Number of Disc Areas) and Change from Baseline as Demonstrated by Fluorescein Angiography in the Study Eye at Scheduled Visits	PP Set
Safety Analyses		
14.3.1.1	Overall Summary of Treatment-Emergent Adverse Events	Safety Set
14.3.2.1	Summary of All Ocular Treatment-Emergent Adverse Events by System Organ Class and Preferred Term	Safety Set
14.3.2.2	Summary of All Non-Ocular Treatment-Emergent Adverse Events by System Organ Class and Preferred Term	Safety Set

Table Number	Title	Set
14.3.3.1	Summary of All Ocular Treatment-Emergent Adverse Events Suspected to be Related to Investigational Medicinal Product by System Organ Class and Preferred Term	Safety Set
14.3.3.2	Summary of All Non-Ocular Treatment-Emergent Adverse Events Suspected to be Related to Investigational Medicinal Product by System Organ Class and Preferred Term	Safety Set
14.3.4.1	Summary of All Ocular Serious Treatment-Emergent Adverse Events by System Organ Class and Preferred Term	Safety Set
14.3.4.2	Summary of All Non-Ocular Serious Treatment-Emergent Adverse Events by System Organ Class and Preferred Term	Safety Set
14.3.5	Summary of All Adverse Events of Special Interest by System Organ Class and Preferred Term	Safety Set
14.3.6.1	Summary of All Ocular Treatment-Emergent Adverse Events Leading to Subject Withdrawal by System Organ Class and Preferred Term	Safety Set
14.3.6.2	Summary of All Non-Ocular Treatment-Emergent Adverse Events Leading to Subject Withdrawal by System Organ Class and Preferred Term	Safety Set
14.3.7.1	Summary of Ocular Treatment-Emergent Adverse Events by Maximum Severity, System Organ Class and Preferred Term	Safety Set
14.3.7.2	Summary of Non-Ocular Treatment-Emergent Adverse Events by Maximum Severity, System Organ Class and Preferred Term	Safety Set
14.3.8.1	Summary of Slit Lamp Biomicroscopy	Safety Set
14.3.8.2.1	Shift in Overall Results of Slit Lamp Biomicroscopy	Safety Set
14.3.8.2.2	Shift in Slit Lamp Biomicroscopy Anterior and Vitreous Chamber	Safety Set

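### The three relatedness categories leave no place for an event with plausible timing and no known response pattern, so the drug-related AE rows could be too low

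*Protocol*

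**What the plan says.** Protocol 7.2.1.2.4 makes an attribution mandatory for each reported adverse event and introduces a closed list: "The three attribution categories are" *Definite*, *Possibly* and *Unrelated*. The conditions that matter here are these.

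- *Definite*: the event "follows a temporal sequence from administration of the study agent; follows a known response pattern to study agent". It must also be confirmed on stopping and on re-exposure where that is appropriate, and have no other reasonable explanation.
- *Possibly*: the event "follows a reasonable temporal sequence from administration of study agent and follows a known response pattern to the study agent", but the clinical state or another therapy could also have produced it.
- *Unrelated*: "An adverse event that does not follow a reasonable temporal sequence after administration of the study agent and most likely is explained by" the disease state or other therapies.

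The lead-in gives general guidance: "The attribution should take into account both the temporal association and any known physical, physiological, or toxicological information regarding the study agent". It has no rule for an event whose pattern is not known.

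SAP 16.1 repeats the three labels without defining them. It then plans drug-related rows in the overall TEAE summary: drug-related TEAEs, drug-related Grade 3/4/5 TEAEs, drug-related serious TEAEs, and drug-related TEAEs leading to discontinuation. SAP 24 adds Tables 14.3.3.1 (ocular) and 14.3.3.2 (non-ocular) for events "Suspected to be Related to Investigational Medicinal Product by System Organ Class and Preferred Term". The SAP does not say which labels count as drug-related. SAP 9.1 imputes only dates, so no rule covers an attribution left blank.

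**The concern.** A reaction not seen before is one that a safety assessment should be able to flag as possibly caused by the drug. Under these definitions it cannot be flagged. Both related categories exclude it because its pattern is not known, and the third excludes it because its timing is reasonable. The rater must still choose a category and has no unlikely, probable or unknown option.

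The study has no control group (Protocol 10.1), so event rates cannot be compared between arms. The drug-related summaries rest entirely on the individual attribution. If the definitions are followed to the letter, those summaries can lose events through this gap and cannot gain any.

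**Working it through.** The plan states no figure on this point, so there is nothing to reproduce. The check sets the three definitions side by side as conditions and looks for combinations that none of them covers.

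Inputs, all from Protocol 7.2.1.2.4, each coded yes or no:

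- T: reasonable timing
- K: known response pattern
- A: plausible other explanation
- R: de-/rechallenge confirmed, or not applicable

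The definitions become:

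- *Definite* = T and K and R and not A
- *Possibly* = T and K and A
- *Unrelated* = not T and A

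Four yes/no conditions give 2 × 2 × 2 × 2 = 16 combinations.

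| T | K | A | R | Category met | Combinations |
|---|---|---|---|---|---|
| yes | yes | yes | either | *Possibly* | 2 |
| yes | yes | no | yes | *Definite* | 1 |
| yes | yes | no | no | none | 1 |
| yes | no | either | either | none | 4 |
| no | either | yes | either | *Unrelated* | 4 |
| no | either | no | either | none | 4 |

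The total is 2 + 1 + 1 + 4 + 4 + 4 = 16. The fourth row is the point: all 4 combinations with reasonable timing and no known pattern meet no category, whatever A and R are.

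The coding treats the other explanation as one condition, although the definitions word it with different strengths. This does not affect the fourth row, which fails *Definite* and *Possibly* on K alone and *Unrelated* on T alone.

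**Effect on the outputs.** An event in the fourth row is neither *Definite* nor *Possibly*. Whether it is recorded as *Unrelated* or left blank, it adds 0 to every drug-related row, and nothing in the SAP restores it.

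**Scale, on assumed rates only.** Let p be the share of subjects with such an event, and take the 30 enrolled subjects of Protocol 10.5. The expected number left out is 30 × p, and the chance of at least one is 1 − (1 − p)^30.

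| Assumed p | Expected subjects | Chance of at least one |
|---|---|---|
| 3% | 0.9 | 60% |
| 5% | 1.5 | 79% |
| 10% | 3.0 | 96% |
| 20% | 6.0 | 99.9% |

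None of these rates is in the documents. The figures are the loss if every rater applies the wording mechanically.

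**Test of the remedy.** Deleting K from *Possibly* places T = yes, K = no, A = yes (2 combinations) in that category. It does not place T = yes, K = no, A = no (2 combinations), because *Possibly* also expects another possible cause; a clarifying sentence is needed for those. The same sentence covers T = yes, K = yes, A = no, R = no (1 combination). Changing the conjunction to *or* would fail: T = no, K = yes, A = yes (2 combinations) would then meet both *Possibly* and *Unrelated*.

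**The case against.** The strongest reply is that the gap is formal and raters will close it themselves. The gloss on *Possibly* says the event might be related, which is where a sensible investigator would put an unfamiliar event with plausible timing. The lead-in also admits physiological and toxicological knowledge, so a known pattern need not mean a previously reported clinical event. This stands in part. It narrows the gap and makes the direction of error conditional on how raters behave. It does not repair the definition: an event that matches no known mechanism or toxicology still falls outside, and the rater has to ignore a stated condition to classify it.

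Four stronger readings are tempting, and the documents do not support them.

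- *That a literal reader is pushed to Unrelated.* A literal reader is barred from that category too, because the timing is reasonable.
- *That novel reactions go uncounted or that the secondary endpoint is compromised.* The endpoint is incidence, seriousness and severity (Protocol 4.2, SAP 3.2); relatedness is not part of it. Such an event still enters the overall TEAE counts, the tables by system organ class and by maximum severity, and the listings. The SAE tables (14.3.4.1 and 14.3.4.2) and the AESI table (14.3.5) are not restricted by relatedness. SAEs are reported within 24 hours whatever their attribution, and AESIs are expedited (Protocol 7.2.1.2.7).
- *That the agent has little clinical experience.* Protocol 2.2 says "there is no published clinical data supporting the therapeutic use of CCR3 in wAMD", which concerns published evidence of benefit, not safety exposure. Protocol 2.3.1 refers to an earlier trial in wAMD subjects, and part of that section is not shown, so what counts as a known pattern cannot be judged here.
- *That the interim safety decision depends on the related counts.* Protocol 10.4.4 and SAP 18 refer to accumulated AE information and relevant safety problems, and set no related-event threshold.

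**Conclusion.** The three definitions are not exhaustive. An event with plausible timing and no known response pattern meets none of them, and neither the lead-in nor the SAP supplies a rule. Applied as written, such an event cannot be counted as drug-related, so the drug-related rows of the overall TEAE summary and Tables 14.3.3.1 and 14.3.3.2 could be too low.

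A reader might infer that these counts are biased downward as a fact. The documents support only that they could be, if raters apply the conditions literally. The size cannot be derived, and the scale figures above rest on assumed rates. The safety analyses are descriptive, in about 30 subjects. This is a faulty rule that is cheap to correct. It does not threaten the study's overall safety reporting.

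**What to change.** In Protocol 7.2.1.2.4:

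- Delete the known-response-pattern condition from *Possibly*. Do not change *and* to *or*.
- Add that an event with reasonable timing that does not meet *Definite* and cannot be clearly attributed to another cause is *Possibly*.

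In SAP 16.1, state that drug-related means *Definite* or *Possibly*. It would help to say in the same place how a missing attribution is counted.

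Two edge cases remain after these changes, and one line each would settle them: an event with reasonable timing but a clear other cause, and an event with neither reasonable timing nor another explanation.

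The cost is an edit to the protocol, the eCRF guidance and the SAP. No new data, visits or subjects are needed. The downside is that related-event counts may rise slightly.

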7.2.1.2.5 Worsening of Underlying Disease and/or Other Pre-Existing Conditions

Worsening of the underlying disease and/or of other pre-existing conditions will be recorded as an AE/SAE in the eCRF.

7.2.1.2.6 Changes in Safety Evaluations

Changes in vital signs, ECG, physical examination, laboratory test results, and ophthalmic evaluations will be recorded as an AE/SAE in the eCRF if they are judged clinically relevant by the investigator.

7.2.1.2.7 Adverse Events of Special Interest

The following are considered adverse events of special interest (AESI):

- Hepatic injury defined by the following alterations of liver parameters:
For subjects with normal liver function at baseline an elevation of AST and/or ALT \geq 3-fold ULN combined with an elevation of total bilirubin \geq 2-fold upper limit of normal (ULN) measured in the same blood draw sample. Subjects showing these lab abnormalities need to be followed up according to [Section 17.1.2](#).
- Abrupt decrease ($>$ 15 letters lost from baseline) of BCVA
- QTc prolongation ($>$ +50 ms from baseline and $>$ 450 ms)

Protocol-specific AESIs are to be reported in an expedited manner similar to SAEs even if they do not meet any of the criteria for an SAE (see [Section 7.2.1.2.2](#)).

7.2.1.3 Adverse Event and Serious Adverse Event Reporting

All AEs, serious and non-serious, occurring during the course of the clinical trial (i.e., from signing the informed consent through the follow-up period) will be collected, documented, and reported to the sponsor by the investigator on the appropriate eCRF and SAE reporting forms.

For each AE, the investigator will provide the onset date, end date, seriousness, grade, relatedness, treatment required, outcome, and action taken with the study agent. The investigator will determine the grade as defined in [Section 7.2.1.2.3](#) and the causal relationship to the study agent (relatedness) as defined in [Section 7.2.1.2.4](#).

The investigator must report the following events immediately (within 24 hours or the next business day whichever is shorter) to the sponsor or designee (refer to the Lab Manual/ISF for specific instructions): SAEs and non-serious AEs relevant to the reported SAE and protocol-specified AESI.

The investigator does not need to actively monitor subjects for adverse events once the clinical trial has ended. However, if the investigator becomes aware of an SAE(s) that occurred after the subject has completed the clinical trial, it should be reported by the investigator to the sponsor if considered relevant by the investigator.

Any AE occurring during the study must be documented in the subject's medical records and as an AE in the eCRF. Any SAE occurring during the study must be documented in the subject's medical records and as an SAE in the eCRF.

A separate SAE report should be used for each SAE. However, if at the time of initial reporting, multiple SAEs are present that are temporally and/or clinically related, they may be reported on the same SAE report.

The investigator should attempt to establish a diagnosis of the event (that meets the definition of an AE or SAE) based on signs, symptoms, and/or other clinical information. In such cases, the diagnosis should be documented as the AE and/or SAE and not the individual signs or symptoms. The diagnosis will become the basis for the verbatim term as reported by the investigator. If no diagnosis is known and clinical signs and symptoms are not present, the abnormal finding should be recorded.

The investigator will take all appropriate and necessary therapeutic measures required for resolution of the AE. Any medication necessary for the treatment of an AE must be recorded on the concomitant medication case report form.

The SAE report(s) should be completed as thoroughly as possible and signed by the investigator or his/her designee before transmittal to the sponsor or designee (e.g., study CRO). It is very important that the investigator provide his/her assessment of relatedness to the study agent as well as an applicable diagnosis at the time of the initial SAE report.

7.2.2 SAFETY LABORATORY EVALUATIONS

Blood samples and urine must be collected at every visit. Safety laboratory examinations will include hematology, biochemistry, coagulation and qualitative urine analysis.

- Hematology: hemoglobin, red blood cell count (RBC), white blood cell count (WBC) with differential, platelets
- Biochemistry: glucose, sodium, potassium, calcium, inorganic phosphate, creatinine, aspartate aminotransferase (AST), alanine aminotransferase (ALT), alkaline phosphatase (AP), lactate dehydrogenase (LDH), total bilirubin (if elevated provide direct bilirubin), urea, total protein, albumin, uric acid
- Coagulation: activated partial thromboplastin time (aPTT), prothrombin time (PT)/international normalized ratio (INR)
- Urine: potential of hydrogen (pH), glucose, erythrocytes, leukocytes, protein, nitrite

Glomerular filtration rate (GFR) will be estimated by the Cockcroft Gault Formula utilizing serum creatinine (see [Section 17.5](#)). All safety laboratory measurements will be performed by a central laboratory. Investigators will get guidance and instructions on laboratory sampling and processing through a separate Lab Manual provided by the central laboratory.

The investigator is responsible for determining and documenting if out of range laboratory values are clinically significant or not. All clinically significant values will be recorded as AEs in the eCRF and followed until resolution. Once resolved, the appropriate eCRF page(s) will be updated.

7.2.3 ELECTROCARDIOGRAM

Twelve-lead ECGs (I, II, III, aVR, aVL, aVF, V1 - V6) will be recorded using a computerized electrocardiograph. The ECGs will be recorded for a 10-second duration after the subjects have rested for at least 5 minutes in a supine position (see [Section 15.1, Schedule of Events Table](#), for time points). ECGs will be stored in the subject's medical records. ECGs may be repeated for quality reasons and the repeat ECG will

be used for analysis. Additional ECGs may be collected by the investigator for safety reasons. Abnormal findings will be reported as AEs (during the trial) or baseline conditions (at screening) in the eCRF.

7.2.4 VITAL SIGNS AND PHYSICAL EXAMINATION

7.2.4.1 Vital Signs

Vital signs (blood pressure, pulse rate and respirations) and temperature will be recorded according to [Section 15.1, Schedule of Events Table](#).

7.2.4.2 Physical Examination

A general physical examination including height (measured only at screening) and weight will be performed according to the time points in [Section 15.1, Schedule of Events Table](#). Whenever possible, the same health care practitioner should perform this examination.

7.2.5 OTHER OPHTHALMIC EXPLORATORY ENDPOINTS AND EVALUATIONS

The ophthalmic endpoints described below as being evaluated over time will be measured in an exploratory manner to investigate the extent, onset, and duration of action without specific inferential testing at any time point. The same is valid for endpoints described as change from baseline.

- CST as measured by SD-OCT, absolute and as change from baseline
- Presence and height of IRF by SD-OCT over time, absolute and as change from baseline
- Presence and height of SRF by SD-OCT over time, absolute and as change from baseline
- Presence and height of PED by SD-OCT over time, absolute and as change from baseline
- Neovascular leakage as demonstrated by fundus photography/FA, absolute and as change from baseline
- Vascular area measured by SD-OCT and fundus photography/FA, absolute and as change from baseline

7.2.5.1 Optical Coherence Tomography

The retinal layers and thickness can be visualized and measured by OCT. The study eye will be investigated by a trained person using only specified OCT equipment. A detailed manual for OCT image acquisition and data transmission will be provided in the ISF. The reported CST will be exclusive of the sub-RPE layer fluid.

7.2.5.2 Fundus Photography/Fluorescein Angiography

The retinal vasculature of the study eye will be evaluated and imaged by fundus photography/FA. A detailed manual for fundus photography/FA will be provided in the ISF.

7.2.5.3 Slit Lamp and Intraocular Pressure Measurement

The slit lamp examination is to be performed in both eyes. The anterior and posterior segment of the eye should be assessed. The results will be entered in the eCRF. IOP will be measured using applanation Goldmann tonometry in both eyes during each visit. The results will also be entered in the eCRF.

7.2.6 STUDY AGENT CONCENTRATION AND PHARMACOKINETICS

Plasma concentration measurements of ALK4290 will be collected to assess systemic exposure to the study agent. For sampling time points and further details, please refer to [Section 17.3](#).

